6.3.5. Death Events

In addition, all deaths will require a specific death data collection tool to be completed. The death data collection tool includes questions regarding cardiovascular (including sudden cardiac death) and noncardiovascular death.

This information should be recorded in the specific death eCRF within one week of when the death is first reported.

6.3.6. Pregnancy

A urine pregnancy test will be performed for all females of child bearing potential prior to enrollment, during each scheduled study visit prior to the injection of investigational product, and during the Exit/Early Withdrawal Visit.

Any pregnancy that occurs during study participation must be reported using a clinical trial pregnancy form. To ensure subject safety, each pregnancy must be reported to GSK within 2 weeks of learning of its occurrence. The pregnancy must be followed up to determine outcome (including premature termination) and status of mother and child. Pregnancy complications and elective terminations for medical reasons must be reported as an AE or SAE. Spontaneous abortions must be reported as an SAE.

Any SAE occurring in association with a pregnancy, brought to the investigator's attention after the subject has completed the study and considered by the investigator as possibly related to the study treatment, must be promptly reported to GSK.

6.3.7. Time Period and Frequency of Detecting AEs and SAEs

The investigator or site staff is responsible for detecting, documenting and reporting events that meet the definition of an AE or SAE.

AEs will be collected from the start of study treatment and until the follow up contact.

SAEs will be collected over the same time period as stated above for AEs. However, any SAEs assessed **as related** to study participation (e.g., study treatment, protocol-mandated procedures, invasive tests, or change in existing therapy) or related to a GSK concomitant medication, will be recorded from the time a subject consents to participate in the study up to and including any follow up contact. All SAEs will be reported to GSK within 24 hours, as indicated in Section [6.3.9](#).

6.3.8. Method of Detecting AEs and SAEs

Care must be taken not to introduce bias when detecting AEs and/or SAEs. Open-ended and non-leading verbal questioning of the subject is the preferred method to inquire about AE occurrence. Appropriate questions include:

“How are you feeling?” or for paediatric studies, “How does your child seem to feel?”

“Have you had any (other) medical problems since your last visit/contact?” or for paediatric studies, “Has your child had any (other) medical problems or seem to act differently in any way since his/her last visit/contact?”

“Have you taken any new medicines, other than those provided in this study, since your last visit/contact?” or for paediatric studies, “Has your child needed to take any medicines, other than those provided in this study, since his/her last visit/contact?”

6.3.9. Prompt Reporting of Serious Adverse Events and Other Events to GSK

SAEs, pregnancies, medical device incidents, and liver function abnormalities meeting pre-defined criteria will be reported promptly by the investigator to GSK as described in the following table once the investigator determines that the event meets the protocol definition for that event.

The investigator is obligated to assess the relationship between investigational product and the occurrence of each AE/SAE. A "reasonable possibility" is meant to convey that there are facts/evidence or arguments to suggest a causal relationship, rather than a conclusion that a relationship to the investigational product cannot be ruled out. The investigator will use clinical judgment to determine the relationship. Alternative causes, such as natural history of the underlying diseases, concomitant therapy, other risk factors, and the temporal relationship of the event to the investigational product will be considered and investigated. The investigator will also consult the Investigator Brochure (IB) to assist in the determination of his/her assessment.

Type of Event	Initial Reports		Follow-up Information on a Previous Report	
	Time Frame	Documents	Time Frame	Documents
All SAEs	24 hours	"SAE" data collection tool	24 hours	Updated "SAE" data collection tool
Cardiovascular or death event	Initial and follow up reports to be completed within one week of when the cardiovascular event or death is reported	"CV events" and/or "death" data collection tool(s) if applicable	Initial and follow up reports to be completed within one week of when the cardiovascular event or death is reported	Updated "CV events" and/or "death" data collection tool(s) if applicable
Pregnancy	2 weeks	"Pregnancy Notification Form"	2 weeks	"Pregnancy Follow-up Form"
Liver chemistry abnormalities for Phase I to IV:				
ALT \geq 3xULN and Bilirubin \geq 2xULN (>35% direct) (or ALT \geq 3xULN and INR>1.5, if INR measured) ¹	24 hours ²	"SAE" data collection tool. "Liver Event CRF" and "Liver Imaging" and/or "Liver Biopsy" CRFs, if applicable ³	24 hours	Updated "SAE" data collection tool/"Liver Event" Documents ³
Remaining liver chemistry abnormalities Phase III to IV:				
ALT \geq 8xULN; ALT \geq 3xULN with hepatitis or rash or \geq 3xULN and <5xULN that persists \geq 4 weeks	24 hours ²	"Liver Event" Documents (defined above) ³	24 hours	Updated "Liver Event" Documents ³

Type of Event	Initial Reports		Follow-up Information on a Previous Report	
	Time Frame	Documents	Time Frame	Documents
ALT \geq 5xULN plus bilirubin <2xULN	24 hours ²	“Liver Event” Documents (defined above) do not need completing unless elevations persist for 2 weeks or subject cannot be monitored weekly for 2 weeks ³	24 hours	Updated “Liver Event” Documents, if applicable ³
ALT \geq 5xULN and bilirubin <2xULN that persists \geq 2 weeks	24 hours ²	“Liver Event” Documents (defined above) ³	24 hours	Updated “Liver Event” Documents ³
ALT \geq 3xULN and <5x ULN and bilirubin <2xULN	24 hours ²	“Liver Event” Documents (defined above) do not need completing unless elevations persist for 4 weeks or subject cannot be monitored weekly for 4 weeks ³	24 hours	Updated “Liver Event” Documents, if applicable ³

1. INR measurement is not required; if measured, the threshold value stated will not apply to patients receiving anticoagulants.
2. GSK must be contacted at onset of liver chemistry elevations to discuss subject safety
3. Liver Event Documents (i.e., “Liver Event CRF” and “Liver Imaging CRF” and/or “Liver Biopsy CRF”, as applicable) should be completed as soon as possible.

The method of recording, evaluating and follow-up of AEs and SAEs plus procedures for completing and transmitting SAE reports to GSK are provided in the SPM. Procedures for post-study AEs/SAEs are provided in the SPM.

6.3.9.1. Regulatory Reporting Requirements for SAEs

Prompt notification of SAEs by the investigator to GSK is essential so that legal obligations and ethical responsibilities towards the safety of subjects are met.

GSK has a legal responsibility to notify both the local regulatory authority and other regulatory agencies about the safety of a product under clinical investigation. GSK will comply with country specific regulatory requirements relating to safety reporting to the regulatory authority, Institutional Review Board (IRB)/Independent Ethics Committee (IEC) and investigators.

Investigator safety reports are prepared for suspected unexpected serious adverse reactions according to local regulatory requirements and GSK policy and are forwarded to investigators as necessary.

An investigator who receives an investigator safety report describing a SAE(s) or other specific safety information (e.g., summary or listing of SAEs) from GSK will file it with the IB and will notify the IRB/IEC, if appropriate according to local requirements.

6.3.10. Other Safety Outcomes

6.3.10.1. Laboratory Assessments

All protocol required laboratory assessments, as defined in the Time and Events Table ([Appendix 1](#) Time and Events Table), will be taken pre-dosing and will be sent to the central laboratory, Quest Diagnostics for analysis (details provided in the SPM). Laboratory assessments must be conducted in accordance with the Central Laboratory Manual and Protocol Time and Events Schedule. Laboratory requisition forms must be completed and samples must be clearly labelled with the subject number, protocol number, site/centre number, and visit date. Details for the preparation and shipment of samples will be provided by Quest Diagnostics. Reference ranges for all safety parameters will be provided to the site by Quest Diagnostics. The central laboratory will fax laboratory results to the Investigator and will transmit the results electronically to GSK.

At the discretion of the Investigator, additional samples may be taken for safety reasons. If additional non-protocol specified laboratory assessments are performed at the institution's local laboratory and result in a change in patient management or are considered clinically significant by the investigator (e.g., SAE or AE or dose modification) the results must be recorded in the subject's CRF. Refer to the SPM for appropriate processing and handling of samples to avoid duplicate and/or additional blood draws.

6.3.10.2. Physical Examination

A detailed physical examination including, but not limited to, an evaluation of the lungs and cardiovascular system will be conducted as outlined in Time and Events Table ([Appendix 1](#) Time and Events Table). For the US, licensed practitioners who are listed on the Form 1572 can complete the physical examination. A licensed physician on the Form 1572 must sign off on the physical examinations completed by non-physicians. In countries outside of the US, the physical examination should be conducted by a medically qualified person; however, if the physical examination is conducted by non-physicians, a medically qualified person must sign off.

Results of the examinations will be recorded in the subject's clinic notes. The same person should perform both examinations, if possible.

6.3.10.3. Vital Signs

Sitting pulse rate and blood pressure measurements will be performed by the investigator or qualified site staff as outlined in Time and Events Table ([Appendix 1 Time and Events Table](#)). Measurements will be done pre-injection with the subject sitting, having rested in this position for at least 5 minutes before each reading. They will be taken before measurement of any clinic lung function tests or ECGs at the specified time point.

At the baseline visit, height and weight will also be measured.

6.3.10.4. Twelve-lead electrocardiogram

Twelve-lead ECGs will be performed at the visits specified in the Time and Events Table ([Appendix 1 Time and Events Table](#)).

Investigators will be provided with ECG machines by GSK through a designated central laboratory. Paper ECG traces will be recorded at a standard paper speed of 25mm/sec and gain of 10mm/mV, with a lead II rhythm strip. There will be electronic capture and storage of the data by a validated method, with subsequent transferral to the central laboratory for manual reading and calculation of the electrocardiographic parameters. Paper traces are required to be maintained at the site with other source documents.

Electrocardiogram measurements will be made after the subject has rested in the supine position for 5 minutes. The ECG should be obtained before lung function testing followed by other study procedures. Collection shortly after a meal or during sleep should be avoided since QT prolongation can occur at these times.

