Patients with severe asthma have significant morbidity and mortality risk; they contribute disproportionately to health care and societal costs of the disease with particularly high costs occurring in those with frequent exacerbations. In MEA112997, subjects had features of severe, refractory asthma, as described in the American Thoracic Society (ATS) workshop on refractory asthma [ATS, 2000], and also demonstrated markers of eosinophilic inflammation [Pavord, 2012]. Together, these criteria were useful to identify a severe eosinophilic asthma population that continued to exacerbate despite maximal therapy with currently marketed asthma medications. This severe, eosinophilic population is the subset of asthmatics most likely to benefit from treatment with mepolizumab.

Subjects who are eligible for participation in 201312 will be subjects who have life-threatening or seriously debilitating asthma, who have been previously treated with mepolizumab, and who have demonstrated clear clinical benefit from the treatment. Subjects entering 201312 through MEA115588 and MEA115661 could have been treated for up to 20 months. Subjects entering the study through MEA115575 and MEA115661

could have been treated for up to 18 months. At a minimum, subjects entering the study will have already been treated for at least 12 months.

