
Potential risk for adverse cardiovascular (CV) effects
	
Mepolizumab binding was restricted to human lymphoid tissues in an immunohistochemistry tissue binding study suggesting a low likelihood of non-pharmacologic effects on cardiovascular (CV) function.
 
No AEs concerning cardiac conduction or repolarization evident in cynomolgus monkeys at doses at least 10-fold in excess of humans dosed at 10 mg/kg or 750 mg.
 
No clinically relevant trends observed in ECG data in humans.
 
In one study in subjects with severe refractory asthma, cardiac events were reported in similar frequencies across treatment groups with a small numerical increase observed in serious ischemic cardiac events in the mepolizumab-treated groups. However, an integrated safety analysis of all placebo-controlled multiple dose asthma trials showed similar frequency of SAEs reported overall from the cardiac and vascular system organ class (SOC).
	
Daily monitoring of SAE by medical monitor; regular systematic review of AE/SAE data from ongoing studies by a GSK safety review team.
 
CV monitoring for study includes:
 
 • ECG monitoring during the trial • Use of standardized CRFs to collect relevant data on CV events of interest (i.e., myocardial infarction, hospitalization for unstable angina and congestive heart failure, arterial thrombosis, pulmonary embolism and deep vein thrombosis); • Adjudication of cardiovascular events

Potential Risk of Clinical Significance	Data/Rationale for Risk	Mitigation Strategy
	
Additionally, similar findings were observed in other SOC with thrombotic events (e.g., stroke in the Nervous System SOC). Data from 2 subsequently completed placebo-controlled severe asthma trials did not show an increased risk of serious ischemic cardiac events; there were no new reports in any treatment groups including placebo.
	

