4.4.3.1.1. ECGs

Discontinuation is required if any of the following ECG criteria are met during the study:

- QTcF >500 msec
- Uncorrected QT >600 msec

These criteria should be based on the average QTc(F) value of triplicate ECGs. For example, if an ECG demonstrates a prolonged QT interval, obtain two more ECGs over a brief period, and then use the averaged QTc(F) values of the three ECGs to determine whether the patient should be discontinued from the study.

For subjects with underlying Bundle Branch Block:

Baseline QTc(F) with Bundle Branch Block	Discontinuation QTc(F) with Bundle Branch Block
<450 msec	>500 msec
450-480 msec	≥ 530 msec

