6.3. Safety

- Incidence of adverse events including systemic (i.e., allergic/IgE mediated and non-allergic) and local site injection-related reactions reported throughout the treatment period.
 - Systemic reactions can be allergic or non-allergic in nature and are typically mild to moderate in intensity, generally develop within several hours of the injection, and are most commonly associated with a complex of symptoms including chills, fever, nausea, vomiting, asthenia, headache, skin rash, pruritus, urticaria, arthralgia/myalgia, hypotension/hypertension, dizziness, bronchospasm, dyspnea or cough.
 - Anaphylaxis, the most severe form of hypersensitivity reactions will be assessed using the diagnostic criteria outlined by the 2006 Joint NIAID/FAAN Second Symposium on Anaphylaxis [[Sampson, 2006](#); [Appendix 6 Anaphylaxis Criteria](#)].
- A 12-lead ECG will be performed to derive the following endpoints:
 - Mean change from baseline in the QTc(F) (QT interval corrected by Friderica's method)
 - Mean change from baseline in QTc(B) (QT interval corrected by Bazett's method)
 - Maximum change from baseline for QTc(F) and QTc(B)
- Clinical laboratory parameters
- Vital signs

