11.1 Appendix 1: Time and Events Table (Continued)

Procedures	Treatment Period (Visit Window is \pm 1 week)														
	17	18	19	20	21	22	23	24	25	26	27	28	29	30	31
Week of study	64	68	72	76	80	84	88	92	96	100	104	108	112	116	120
Safety Assessments															
Concomitant Medication	X	X	X	X	X	X	X	X	X	X	X	X	X	X	X
Physical Examination															
Vital Signs	X	X	X	X	X	X	X	X	X	X	X	X	X	X	X
12-lead ECG			X						X						
Adverse Events	X	X	X	X	X	X	X	X	X	X	X	X	X	X	X
Serious Adverse Events	X	X	X	X	X	X	X	X	X	X	X	X	X	X	X
Laboratory Assessments²															
Immunogenicity									X						
Hematology			X						X						X
Chemistry			X						X						X
Liver Analytes			X						X						X
Pregnancy Test ³	U	U	U	U	U	U	U	U	U	U	U	U	U	U	U
Efficacy Assessments															
Exacerbation review	X	X	X	X	X	X	X	X	X	X	X	X	X	X	X
Asthma Control Questionnaire-5			X			X			X			X			X
Spirometry			X						X						X
Worksheets/IP/eCRF															
Administer Mepolizumab 100mg SC	X	X	X	X	X	X	X	X	X	X	X	X	X	X	X
Dispense paper worksheet	X	X	X	X	X	X	X	X	X	X	X	X	X	X	X
Collect paper worksheet	X	X	X	X	X	X	X	X	X	X	X	X	X	X	X
Register IVRS/IWRS	X	X	X	X	X	X	X	X	X	X	X	X	X	X	X
Complete eCRF	X	X	X	X	X	X	X	X	X	X	X	X	X	X	X

2. All laboratory assessments to be completed prior to dosing
3. Pregnancy test (all females of childbearing potential) U = Urine

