11.1 Appendix 1: Time and Events Table (Continued)

Procedure	Treatment Period (Visit Window is \pm 1 Week)												Exit/ EW Visit ⁴
	32	33	34	35	36	37	38	39	40	41	42	43	
Week of study	124	128	132	136	140	144	148	152	156	160	164	168	172
Safety Assessments													
Concomitant Medication	X	X	X	X	X	X	X	X	X	X	X	X	X
Physical Examination													X
Vital Signs	X	X	X	X	X	X	X	X	X	X	X	X	X
12-lead ECG						X				X			X
Adverse Events	X	X	X	X	X	X	X	X	X	X	X	X	X
Serious Adverse Events	X	X	X	X	X	X	X	X	X	X	X	X	X
Laboratory Assessments²													
Immunogenicity						X							X
Hematology						X						X	X
Chemistry						X						X	X
Liver Analytes						X						X	X
Pregnancy Test ³	U	U	U	U	U	U	U	U	U	U	U	U	U
Efficacy Assessments													
Exacerbation review	X	X	X	X	X	X	X	X	X	X	X	X	X
Asthma Control Questionnaire-5			X			X			X			X	X
Spirometry						X						X	X
Worksheets/IP/eCRF													
Administer Mepolizumab 100mg SC	X	X	X	X	X	X	X	X	X	X	X	X	X
Dispense Paper Worksheet	X	X	X	X	X	X	X	X	X	X	X	X	X
Collect Paper Worksheet	X	X	X	X	X	X	X	X	X	X	X	X	X
Register IVRS/IWRS	X	X	X	X	X	X	X	X	X	X	X	X	X
Complete eCRF	X	X	X	X	X	X	X	X	X	X	X	X	X

2. All laboratory assessments to be completed prior to dosing

3. Urine pregnancy test for all females of childbearing potential, U = Urine

4. In the event a subject withdraws early at a scheduled visit, all study procedures scheduled for the Exit Visit (Visit 44) should be performed at this visit instead. In the event a subject withdraws between visits, the subject should be asked to return to the clinic as soon as possible to complete the Exit Visit procedures.

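### Moving the pre-Exit 12-lead ECG to Week 120 would cut the longest scheduled ECG interval from 48 to 28 weeks: a minor, cheap scheduling improvement

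*Protocol*

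**What the plan says.** Protocol 6.3.10.4 sets no ECG frequency of its own: "Twelve-lead ECGs will be performed at the visits specified in the Time and Events Table". The schedule is therefore whatever Appendix 1 shows. Read by column, its ECG row is marked at Weeks 0, 24, 48, 72, 96 and 144, at one visit between Week 144 and Exit (Week 160 as it reads, possibly Week 168), and at Exit (Week 172).

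Week 120 (Visit 31) has no ECG mark, although hematology, chemistry, liver analytes, ACQ-5 and spirometry are all marked there. The schedule in SAP 11.1 agrees that Week 120 has no ECG.

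Four other provisions bear on this:

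- Footnote 4 of the table covers early leavers. For a subject who withdraws at a scheduled visit, "all study procedures scheduled for the Exit Visit (Visit 44) should be performed at this visit instead", and those procedures include an ECG. A subject who withdraws between visits is asked back for the same procedures.
- Protocol 4.4.3.1.1 makes stopping mandatory on QT findings: "Discontinuation is required if any of the following ECG criteria are met during the study". The general thresholds are QTcF above 500 msec or uncorrected QT above 600 msec.
- Protocol Table 1 (Section 1.3.1) lists "ECG monitoring during the trial" as one of three cardiovascular monitoring measures.
- ECG parameters are a secondary endpoint. Protocol 6.3 includes "Maximum change from baseline for QTc(F) and QTc(B" among the derived measures, and SAP 11.5.4 and Tables 2.61 to 2.63 summarise ECG values and QTc categories, by scheduled visit.

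**The concern.** The ECG row follows the same 24-week rhythm as the bloods and spirometry up to Week 96. It then skips one step that those assessments keep, and no reason is given. Between Weeks 96 and 144 the QT stopping rule can act only on an unscheduled or early-withdrawal ECG, and continuing subjects contribute no scheduled value to the by-visit summaries or to the maximum QTc change.

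The late ECG, by contrast, sits close to another one and where fewest subjects can reach it. SAP 11.6.1 expects subjects to leave before the Exit Visit because of commercial availability, and everyone who reaches Week 160 or 168 has already passed Week 120. What is at stake is the placing of one ECG, not the validity of any analysis.

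**Working it through.** **Inputs.** ECG weeks come from the protocol Appendix 1 ECG row, and Week 0 is counted as the first ECG. The visit window is ±1 week and dosing is every 4 weeks (Appendix 1). There is no stated ECG interval to reproduce.

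**Interval = next ECG week − previous ECG week.**

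| Schedule | ECG weeks | Intervals (weeks) | Longest | ECGs |
|---|---|---|---|---|
| Now, pre-Exit mark at 160 | 0, 24, 48, 72, 96, 144, 160, 172 | 24, 24, 24, 24, 48, 16, 12 | 48 | 8 |
| Now, pre-Exit mark at 168 | 0, 24, 48, 72, 96, 144, 168, 172 | 24, 24, 24, 24, 48, 24, 4 | 48 | 8 |
| Pre-Exit mark moved to 120 | 0, 24, 48, 72, 96, 120, 144, 172 | 24 (six times), 28 | 28 | 8 |
| Week 144 mark moved to 120 instead | 0, 24, 48, 72, 96, 120, 160, 172 | 24 (five times), 40, 12 | 40 | 8 |
| Week 120 added, nothing removed | 0, 24, 48, 72, 96, 120, 144, 160, 172 | 24 (six times), 16, 12 | 24 | 9 |

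The 48-week interval does not depend on where the pre-Exit mark sits. The mark to move is the pre-Exit one; moving Week 144 would leave 40 weeks.

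**Windows.** Two visits, each up to 1 week off, add up to 2 weeks: 48 + 2 = 50 now, 28 + 2 = 30 after the move.

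**Dosing visits strictly inside the longest interval.** Now, Weeks 100 to 140: (140 − 100)/4 + 1 = 11. After the move, Weeks 148 to 168: (168 − 148)/4 + 1 = 6.

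**By week of leaving**, counting the Exit/early-withdrawal ECG at that week:

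| Leaves at Week | Now: ECGs, longest interval | After the move |
|---|---|---|
| 120 | 6, 24 | 6, 24 |
| 124 | 6, 28 | 7, 24 |
| 140 | 6, 44 | 7, 24 |
| 144 | 6, 48 | 7, 24 |
| 156 | 7, 48 | 8, 24 |
| 168 | 8, 48 (7, 48 if the mark is at 168) | 8, 24 |
| 172 | 8, 48 | 8, 28 |

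**Where early-withdrawal ECGs are reported.** SAP 11.2.2 moves them to the nearest visit at which an ECG was scheduled, if that visit is empty; SAP 11.2.3 assigns assessments after Visit 31 by closest target date. Under the current schedule the midpoint of Weeks 96 and 144 is Week 120. An ECG at Week 124 is 144 − 124 = 20 weeks from Week 144 and 124 − 96 = 28 from Week 96; one at Week 140 is 4 and 44 weeks away. All early-withdrawal ECGs at Weeks 124 to 140 are therefore reported under Week 144.

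**How many subjects.** The documents do not say. Protocol 4.1 gives about 375 eligible. Assuming 10%, 30% or 50% of these stay past Week 120: 0.10 × 375 = 37.5, 0.30 × 375 = 112.5, 0.50 × 375 = 187.5, or about 38, 113 or 188. These are shares of the eligible, not the enrolled, and the full 48 weeks applies only to those who go on to Week 144.

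**The case against.** The strongest case against is that this is preference. Protocol 3.1 sets a 6-monthly rhythm for bloods and spirometry but none for ECGs, so nothing makes 24 or 28 weeks the required interval. That stands, and it limits the point to a suggested improvement.

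Three stronger readings are tempting, and the documents do not support them.

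- A reader might infer a safety gap. Between any two scheduled ECGs, whether 24 or 48 weeks apart, the QT rule depends on unscheduled or withdrawal ECGs. Throughout, adverse events and vital signs are assessed every 4 weeks, cardiovascular events have their own forms and adjudication, and an ECG is due at early withdrawal. Protocol Table 1 reports "No clinically relevant trends observed in ECG data in humans", and Protocol 1.1 says of prior exposure: "At a minimum, subjects entering the study will have already been treated for at least 12 months".
- A reader might infer harm to the ECG endpoint. The summaries are descriptive. Without a Week 120 ECG there is no Week 120 row; nothing planned is missing and no estimate is biased. SAP 11.4.2 also brings unscheduled values into the any-time post-baseline summaries.
- A reader might infer that the swap is free because there are eight ECGs either way. That holds for subjects who reach Week 172. Those who leave after Week 120 and up to the present pre-Exit visit have 7 instead of 6, or 8 instead of 7, and the SAP expects subjects to leave before Exit.

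The position of the pre-Exit mark is also uncertain. On the same table page the dosing row carries a mark in the Exit column although the last dose is at Week 168, so column positions there should be checked. The SAP copy of that page supports three late ECG marks (16 marks for vital signs and ECG together, 13 + 3) but gives no positions. The conclusion is the same for Week 160 or 168.

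The ECG row in the Amendment 03 log differs from the current table; that is no evidence of an error and is not used here.

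**Conclusion.** The point holds as a minor, cheap improvement. Subjects who stay to Week 144 have one 48-week interval without a scheduled ECG, while the pre-Exit ECG comes only 4 weeks (if at Week 168) or 12 weeks (if at Week 160) before the Exit ECG. Moving the latter to Week 120 makes the longest interval 24 weeks for anyone who leaves by Week 168 and 28 for those who reach Week 172. Subjects who leave by Week 120 keep the same intervals.

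This rests on reading the table by column and on counting from Week 0. For subjects whose Visit 1 ECG is copied from the parent study's exit visit up to 8 weeks earlier (SAP 5.2, Definition 1), the first interval can be up to 24 + 8 = 32 weeks, whichever schedule is used. The gain in safety information is modest and the number who would benefit is unknown.

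**What to change.** In protocol Appendix 1 and the SAP 11.1 copy, move the single pre-Exit ECG (Week 160 as the table reads, possibly Week 168), and not the Week 144 one, to Week 120 (Visit 31). The ECG row then reads Weeks 0, 24, 48, 72, 96, 120, 144 and Exit/early withdrawal.

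The cost is one moved mark, by amendment. Subjects who reach Week 172 lose the ECG close to Exit. Subjects who leave after Week 120 and up to the present pre-Exit visit have one more ECG, taken at a visit that already includes bloods and spirometry.

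The move does nothing for subjects already past Week 120. No footnote is needed for them. If one is wanted on SAP Tables 2.61 to 2.63, it should say that, under SAP 11.2.2 and 11.2.3, early-withdrawal ECGs taken at Weeks 124 to 140 are reported under Week 144. A note saying only that unscheduled ECGs exist in that period would not help, because SAP 11.2.3 has every visit after Week 120 collected as unscheduled.
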